7.3.2 RELATIONSHIP TO STUDY INTERVENTION

Unrelated

Possibly related

Related

7.3.3.3 EXPECTEDNESS

Unexpected

Expected (described in the protocol and/or Investigator's Brochure)

7.3.4 TIME PERIOD AND FREQUENCY FOR EVENT ASSESSMENT AND FOLLOW-UP

AE's will be solicited at each study visit, during the scheduled phone contacts and as often as daily via subject report on the questionnaires

Unsolicited AE's may be identified via observations and general discussions with the subject and/or parent at the study visits

7.3.5 ADVERSE EVENT REPORTING

Events will be recorded on the Adverse Event case report form as they are identified

All events will be reported to the sponsor upon identification

All unanticipated events will be reported to the IRB on continuing review applications or close of study (or according to local IRB policy).

Adverse event forms will be sent to the medical monitor every 2 weeks during the study, who will then summarize the AE's in a report to the sponsor and IRB.

7.3.6 SERIOUS ADVERSE EVENT REPORTING

All unanticipated serious adverse events will be reported within 48 hours of identification to the sponsor, medical monitor and the IRB (or as required using local standards)

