6 STUDY INTERVENTION DISCONTINUATION AND PARTICIPANT DISCONTINUATION/WITHDRAWAL

6.1 DISCONTINUATION OF STUDY INTERVENTION

The intervention will be halted by the investigators if:

1. Equivalent or improved in-brace correction is not obtained at the Week 1 visit
2. If the subject is not able/willing to wear the GSM brace for approximately the same number of hours as the TLSO
3. Safety concerns are noted by the PI, study staff and/or the medical monitor
4. Radiographic evaluation at Visit 3 suggests that the curve is not stable (has progressed more than 10 degrees)
5. If the parent/subject, investigator or medical monitor feel that continuation of treatment in the GSM brace is not in the best interests of the subject. Ongoing care will be individually determined based on standard of care considerations.

Once the GSM brace is discontinued, continued follow-up for safety and efficacy are not required.

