7.2.1 DEFINITION OF ADVERSE EVENTS (AE)

The following AE's are anticipated and related or possibly related to brace wear or to the diagnosis of AIS:

- Skin Issues (on the trunk, shoulders or any other area in contact with the brace): bruising, lacerations, ulcers, pressure sores, rash. Most skin issues are classified as mild and can be alleviated by minor adjustments to the brace.
- Back pain
- Anxiety
- Problems sleeping
- Shortness of breath
- Altered body image or self-esteem

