7.3.7 REPORTING EVENTS TO PARTICIPANTS

All moderate or severe, possibly related or related events will be reported to subjects who are currently wearing the GSM brace via a phone call from the PI within 48 hours of identification

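### The 48-hour rule covers only unanticipated serious adverse events, so one of an anticipated kind may reach the medical monitor only with the 2-weekly forms

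*Combined protocol and SAP*

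**What the plan says.** Four parts of the protocol's section 7.3 govern who hears of an event and when.

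- **Fast route (7.3.6).** "All unanticipated serious adverse events will be reported within 48 hours of identification"; the recipients are the sponsor, the medical monitor and the IRB, with the qualifier "or as required using local standards".
- **Routine route to the monitor (7.3.5).** "Adverse event forms will be sent to the medical monitor every 2 weeks during the study". The monitor then summarizes the events for the sponsor and IRB.
- **Route to the sponsor (7.3.5).** "All events will be reported to the sponsor upon identification", with no restriction by seriousness or expectedness.
- **Route to participants (7.3.7).** "All moderate or severe, possibly related or related events will be reported to subjects who are currently wearing the GSM brace", by a call from the PI within 48 hours, whether or not the event was anticipated.

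The anticipated events are in 7.2.1. They include skin problems ("bruising, lacerations, ulcers, pressure sores, rash"), back pain, anxiety, sleep problems, shortness of breath and altered body image. Section 7.3.3.3 defines an expected event as one described in the protocol and/or the Investigator's Brochure. Section 7.2.2 defines a serious event by its outcome, hospitalization among others.

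Section 6.1 leaves halting the intervention to the investigators. One ground is: "Safety concerns are noted by the PI, study staff and/or the medical monitor".

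**The concern.** Whether a serious event reaches the medical monitor quickly depends on the word unanticipated, and the protocol does not say how that word applies when a listed kind of event turns serious. Section 5.2.1 says that most adverse events reported with TLSOs involve loss of skin integrity, and skin problems are on the anticipated list. The exclusion therefore takes in the kind of event that the protocol itself expects from bracing.

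At stake is the timeliness of central safety review. The study is multi-center (3.1), enrolls girls aged 10 to 15 (4.1), and uses a brace that section 1.1 describes as tested so far on healthy volunteers. Apart from the sponsor, the medical monitor is the only named role that receives adverse event forms from the whole study. The monitor's concerns are one ground for halting (6.1), and the monitor's input helps to set the final sample size (8.1). A pattern across sites is what a single site investigator cannot see.

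**Working it through.** The plan gives no figure to reproduce. The check sets the reporting rules side by side and then does simple interval arithmetic.

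**1. Can an event be both serious and anticipated?** Seriousness in 7.2.2 depends on outcome. Anticipation in 7.2.1 and expectedness in 7.3.3.3 depend on the kind of event and on its being described. The skin entry notes that most such problems are mild, but it does not restrict the list to mild ones. A pressure sore, or shortness of breath, that leads to hospitalization therefore meets both definitions on a literal reading.

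**2. Which routes then apply?**

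| Recipient | Unanticipated serious event | Serious event of a listed kind |
|---|---|---|
| Site investigator | on identification | on identification |
| Sponsor | on identification (7.3.5) | on identification (7.3.5) |
| Medical monitor | within 48 hours (7.3.6) | 2-weekly forms (7.3.5) |

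Only the monitor's row differs between these recipients. The 48-hour IRB report is limited in the same way.

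**3. How long is the wait for the monitor?**

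- Limit under 7.3.6: 48 h / 24 = 2 days.
- Longest wait for the batch under 7.3.5: 2 × 7 = 14 days, for an event identified just after a batch has gone.
- Average wait, assuming that events are identified evenly over the cycle: (0 + 14) / 2 = 7 days.
- Difference between the two longest waits: 14 − 2 = 12 days.

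**4. How does this sit with 7.3.7?** If such an event is rated moderate or severe and at least possibly related, current wearers must be told by day 2, while the monitor may not have the form until day 14. At those two limits the monitor learns 14 − 2 = 12 days after the participants. The early call to participants is itself a sound safeguard; the comparison only shows that the monitor's timing is out of step with it.

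**5. Does the wait delay a halt?** No. Under 6.1 the investigators halt the intervention, and a concern from the PI or study staff is enough. Section 6.1 also accepts a best-interests judgement by the parent or subject, and 6.2 lets participants stop at any time. None of these waits for the monitor.

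**The case against.** The strongest counter-argument is that the 48-hour rule already covers these events. Section 5.2.1 says that the device carries no risk that could be classed as serious, the anticipated list stands under the definition of ordinary adverse events, and the protocol describes no serious form of them. On that reading every device-related serious event is unanticipated. The reading is tenable, and the Investigator's Brochure, which is part of the expectedness test, is not available to check. But 7.2.1 and 7.3.3.3 support the opposite reading equally well, and two sites could handle the same event differently. The objection shows that the text is ambiguous; it does not close the gap.

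Second, the local-standards clause may bring faster reporting at some sites. It guarantees nothing to the monitor study-wide.

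Third, 14 days is a worst case, and 5.2.1 calls adverse events with TLSOs rare. Both points are fair and limit the expected impact.

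A reader might go further and infer that the delay holds up the person who can stop treatment. Section 6.1 does not support that: halting belongs to the investigators, whose sites record the events, and the monitor is one of several parties whose concern can prompt it. Nor do the documents say that the monitor is independent of the sponsor, or that brace-related events are the most likely serious ones. The point does not rely on either.

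**Conclusion.** The point holds as a gap in the reporting rule. On a literal reading, a serious adverse event of a listed kind has no stated route to the medical monitor faster than the 2-weekly forms. The cost is a longest wait of 14 days in place of 2, and it falls on the monitor's cross-site review alone.

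This rests on three assumptions: that unanticipated is judged by kind of event rather than by severity, that forms go out on the 2-week schedule, and that no stricter local standard applies. The 7-day average also needs events spread evenly over the cycle. The documents give no rate for serious events, so the number affected cannot be estimated and may be very small. The change is worth making because it is cheap and removes a dependence on an undefined word in an early-use study of minors.

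**What to change.** Split the sentence in 7.3.6 in two. First, require every serious adverse event, anticipated or not, to be reported to the medical monitor and the sponsor within 48 hours of identification. Second, keep the IRB requirement as written, for unanticipated serious events or under local rules, and attach the local-standards clause to that part only.

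The monitor's longest wait for a serious event of a listed kind then falls from 14 days to 2. The sponsor's timing does not change, since 7.3.5 already sends it everything on identification. No new rule for moderate, non-serious events is needed; that would reach well beyond the gap.

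A lesser alternative is to state that an event more severe than described counts as unanticipated. That would settle the ambiguity but leave a judgement to each site.

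The cost is a short protocol amendment and a few extra notifications. Section 8.1 plans for 10 to 30 subjects completing 3 months, with those who exit earlier replaced, so the added workload should be small.

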7.3.7 REPORTING EVENTS TO PARTICIPANTS

All moderate or severe, possibly related or related events will be reported to subjects who are currently wearing the GSM brace via a phone call from the PI within 48 hours of identification

8 STATISTICAL CONSIDERATIONS

8.1 SAMPLE SIZE DETERMINATION

Study-wide, recruitment will continue until at least 10 but no more than 30 subjects have completed 3 months in the GSM brace. The final sample size will depend on an ongoing examination of the results, patient comments, input from medical monitor and the discretion of the sponsor. Therefore, if a subject exits the study prior to that point, another subject will be enrolled. The sample size is appropriate for initial field testing of this device and no sample size calculations were conducted.

8.4 STATISTICAL ANALYSES

This is a pilot study and no formal hypothesis testing will be done.

Descriptive statistics of selected variables will be calculated.

Primary Aims

1. Safety of the GSM brace: Summary of all adverse events; number and nature of adjustments made to the GSM brace
2. Performance of the GSM brace:
 - a. Difference between in-brace Cobb angle measurements obtained in each brace
 - b. Difference in out of brace Cobb angles (pre- and 3 months post-GSM brace)
 - c. Average hours of wear per day relative to the prescription and to historical wear data (from chart and temperature monitor)
 - d. Change in BrQ and ISYQOL scores baseline to 3-month visit; summary of GSM acceptability during various activities and qualitative analysis of free text entries recorded in GSM Brace Diary

Secondary Aims

1. Difference in range-of-motion testing between TLSO and GSM brace
2. Difference in vital capacity testing between TLSO and GSM brace

3. Correlation of accelerometer data and temperature monitor data; development and testing of an algorithm to convert accelerometer data to an estimate of the average hours of wear per day.

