Despite a large body of research literature, the question of TLSO effectiveness wasn’t definitively answered until 2013, when the results of the Bracing in Adolescent Scoliosis Trial (BrAIST) were published.⁷ The use of a TLSO significantly reduced the incidence of curve progression to surgical threshold, relative to no treatment, in both the randomized and observation arms of the study. Additionally, a strong dose-response curve was noted, demonstrating that increasing average hours of wear per day decreases the risk of significant curve progression. The dose-response relationship is supported by several other studies, and evidence is emerging that longer hours of wear are required by younger patients with larger Cobb angles, who are at higher risk of curve progression.⁸⁻¹¹ Unfortunately, clinical experience and objective monitoring of wear time indicates that compliance/adherence is a serious issue in bracing treatment.^{6, 12-14} In the BrAIST study,⁷ the median wear time was 13 hours per day, despite prescription of a minimum of 18 hours per day. Adherence improves when optimal levels of education and support are provided to patients and when barriers, such as comfort and appearance, are addressed.^{9, 15-17}

The amount of Cobb angle correction obtained in the brace has also been linked to treatment outcomes. Historically, the goal has been in-brace correction of at least 50%,^{18, 19} although successful outcomes have been shown with correction ranging from 10-50% or greater.²⁰⁻²⁴ The amount of correction a TLSO can achieve is enhanced by appropriate customization, starting with accurate measurements of both the patient’s trunk and their specific curve pattern and magnitude.²⁵ But the amount of correction achievable from even an optimally designed TLSO is limited by patient and curve characteristics which contribute to the stiffness of the curve. Therefore, comparison of correction between brace designs may best be demonstrated by within-patient differences if randomization to treatment with large samples is not possible.

It is clear that a high percentage of patients experience curve progression and subsequent spinal fusion surgeries which may have been prevented if appropriate corrective forces and adequate wear time had been achieved.

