2 OBJECTIVES AND ENDPOINTS

Primary

1. Safety of the GSM brace: To identify unanticipated adverse events associated with the GSM brace and patient characteristics likely to raise safety issues
2. Performance of the GSM brace:
 - a. To assess immediate radiographic outcomes (in-brace Cobb angle) relative to those in the TLSO
 - b. To assess short-term radiographic outcome (out of brace Cobb angle) after 3 months
 - c. To assess adherence to the bracing prescription (hours of wear per day)
 - d. To assess patient-reported outcomes including health-related quality of life and measures of acceptability of the GSM brace (e.g. comfort, stress, interference with activities) relative to experiences in the patient's previous TLSO

Secondary

1. To assess spinal range of motion in the GSM brace relative to the subject's TLSO
2. To assess lung vital capacity in the GSM brace relative to the subject's TLSO
3. To validate accelerometer data (obtained from an embedded sensor in the GSM brace) as an estimate of the average hours of wear per day.

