Phone Visit and Performance Check (2 weeks after baseline)

1. Study staff will contact the subject and parent/guardian to see how well the subject is adapting to the GSM brace and remind the subject/parent to remove the temperature monitor from the brace and send by courier overnight to the study site.
2. Safety Check: Query for adverse events and other issues
3. Performance Check – to ensure adherence to prescribed number of hours per day in the GSM brace:
 1. If any problems are noted during the phone contact the PI will determine whether adjustments to the brace could alleviate the issues and, if so, ask the subject return to clinic
 2. If the temperature monitor data indicate the subject is wearing the GSM brace an average of 2 or more hours less per day than prescribed
 - a. The PI will determine whether adjustments to the brace could alleviate the issues and have the subject return to clinic; if not, the subject will exit the study and return to their current TLSO
 - b. If after adjustments to the brace, the subject feels that the brace is still incompatible with the prescribed wear time, the subject will exit the study and return to their current TLSO

Phone Visits (Weeks 4, 6, 8, and 10 after baseline)

1. Study staff will contact the subject and parent/guardian to see how well the subject is adapting to the GSM brace and remind the subject/parent to continue completion and return of the diaries to the study site in the prepaid envelopes.
2. Safety Check: Query for adverse events and other issues

Visit 3 (3-4 months after baseline, approximately 1 hour)

1. Standing coronal full-spine radiographs out of the brace and measurement of the Cobb angle
2. Download of temperature monitor data from GSM brace
3. Collection of GSM Brace Diary
4. Completion of the Brace Questionnaire and the Italian Spine Youth Quality of Life (ISYQOL) questionnaire
5. Completion of GSM App Feedback Questionnaire (optional)
6. Safety Check: Query for adverse events and other issues
7. Performance Check:
 - a. If the Cobb angle measures no more than 10 degrees greater than that obtained from the subject's most recent out of brace radiograph (prior to enrollment), we will conclude the curve is stable or has progressed within the expected limit. If not, the subject will resume use of the TLSO.
 - b. If curve stabilization is seen, subjects may opt to continue the GSM brace or resume use of their TLSO based on subject and parent preferences.

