Participating sites who do not have access to the EOS® Imaging system Micro Dose protocol are allowed to use their existing equipment. However, they are responsible for calculating the amount of research-related radiation and the potential risks, to include this information in IRB/human subjects research application materials, and to relate this information to the subject via the informed consent document as required by the IRB or equivalent review board.

In addition to the Cobb angle, other components of the deformity will be measured, including kyphosis, lordosis, apical vertebral rotation, and coronal and sagittal balance.

Spiropet

Vital capacity will be estimated using the Spiropet portable spirometer. Subjects will be instructed to inhale as deeply as possible and to then exhale completely over 5 to 6 seconds through the spirometer. This will be repeated 2 times, with a minimum of 30 seconds in between trials. Disposable mouthpieces are used to prevent contamination across subjects.

<https://www.fitnessmart.com/products/spiro-pet-small-dry-spirometer-model-64450?variant=29708592263>

Temperature Monitors to Estimate Brace Adherence

Participating sites are encouraged to use their standard-of-care brace temperature monitors/loggers. If the site has not been using a monitor to estimate brace wear, the sponsor will provide iButtons and the required hardware/software.

The iButton™ is a commercially available electronic device which records and stores time, date and temperature readings. The logger will be set to record date, time and temperature every 15 minutes. The temperature range at which the brace is assumed to be on will be set at 82.4°F and 110°F. Validation of the accelerometer data as an estimate of the number of hours per day that the subjects are wearing the brace will be done via comparison with data from a temperature logger. The reliability and validity of iButton™ data for estimating wear time has been demonstrated in several published reports.²⁷⁻²⁹ (iButton™ DS1922L”

https://www.thermochron.com/product/ds1921g-thermochron/?gclid=EA1aIQobChMI5t-G1K6G3QIVRMDICh1A2gDSEAAyASAAEgL1YvD_BwE (Maxim Integrated Products, Inc.; [name]).

Questionnaires

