5.1.2 BRACE CUSTOMIZATION, DOSING AND ADMINISTRATION

The GSM braces will be provided directly to the research team by the company at no cost. Each GSM brace will be custom-fabricated via computer-assisted design using the 3D torso scans and a treatment plan (e.g. placement of corrective forces) devised by the treating orthotist as inputs. The brace components are then assembled. Once assembled, the GSM brace will be fit to the subject by representatives of the manufacturer and in consultation with the treating orthotist.

The GSM brace will be prescribed for the same number of hours per day as was the TLSO (generally 18-22 hours per day, individualized based on patient characteristics). Subjects and the family will be shown how to don and doff the brace, how to remove the temperature monitor, and how to exchange and recharge the battery in the GSM sensor board.

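### Secondary objective 3 aims to validate accelerometer-based wear hours, but 8.4 names only a correlation and leaves the test of the conversion algorithm without an error measure or separate test data

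*Combined protocol and SAP*

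**What the plan says.** Section 2 gives the third secondary objective as "To validate accelerometer data (obtained from an embedded sensor in the GSM brace) as an estimate of the average hours of wear per day". Section 7.1 repeats it as a secondary measure. In 5.1.2 Study Procedures, under the temperature monitors, validation "will be done via comparison with data from a temperature logger".

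The analysis in 8.4 is "Correlation of accelerometer data and temperature monitor data; development and testing of an algorithm to convert accelerometer data" into hours. It has two parts:

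- The correlation. Its type and its unit (15-minute reading, subject-day or subject average) are not given.
- The algorithm. No test statistic, acceptable error or separate test sample is given.

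Appendix 1, section 8 sets a closely similar task for the optional substudy: turning each day of smart-pad force values into hours worn, with the temperature monitor as the reference. There the plan does call for calibration plots together with other measures of error. That text covers the smart-pad model only.

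**The concern.** Validating an estimate of hours is a question of agreement in hours: how far the estimate falls from the reference, on average and for an individual. A correlation answers a different question, namely whether the two readings rise and fall together. The step that could answer the right question, testing the algorithm, is left open.

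The stake is the later use of the sensor. Section 1.3 treats the sensor data as informational until the system and its algorithms have been validated, and 3.1 says the pilot will inform refinement of the device and a pivotal trial. If the reported evidence is a correlation plus an algorithm that fits its own development data, readers will not know the error in hours per day that a new patient's estimate would carry.

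**Working it through.** The plan gives no target correlation, agreement limit or sample size calculation for this objective, so there is no figure to reproduce.

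**Inputs from the documents.** 10 to 30 completers (8.1); prescribed wear "generally 18-22 hours per day" (Brace Customization, Dosing and Administration); and, in the bracing trial described in 1.2, "the median wear time was 13 hours per day".

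**Assumptions, not in the documents.** The SD of wear and the SD of sensor noise, shown as ranges. Below, x is monitor hours and y is sensor-estimated hours.

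**1. Shift and scale without noise.** For y = a + b·x with b > 0, r = 1 whatever a and b are. A constant 3 h error gives r = 1.0000. So does a 20% under-read, although it amounts to 0.2 × 13 = 2.6 h, 0.2 × 18 = 3.6 h and 0.2 × 22 = 4.4 h.

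**2. The same with noise.** Simulation of y = a + b·x + e, one pair per subject, 2,000 data sets per setting, n = 10 or 30, mean 13 or 18 h, SD of wear 2 or 4 h, noise SD 0.5 or 1 h. The last column is the single setting n = 30, mean 18 h, SD 4 h, noise 1 h.

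| Error in y | Median r, all settings | Mean difference (h), all settings | 95% limits of agreement (h), one setting |
|---|---|---|---|
| none | 0.90 to 0.99 | 0 | -1.9 to +1.9 |
| constant -3 h | 0.90 to 0.99 | -3.0 | -4.9 to -1.1 |
| 20% under-read | 0.85 to 0.99 | -2.6 to -3.6 | -6.1 to -1.1 |

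The correlation barely separates the rows; the difference in hours does.

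**3. Dependence on the spread of wear.** With unbiased error of SD 1.5 h, r = s / √(s² + 1.5²), where s is the SD of wear:

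- s = 1: 1/√3.25 = 0.55
- s = 3: 3/√11.25 = 0.89
- s = 5: 5/√27.25 = 0.96

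The error in hours is the same each time.

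**4. What the algorithm step changes.** Regressing x on y and using the fitted value removes linear bias. In one simulated set of 30 (mean 18 h, SD 3 h, y = -3 + 0.9x + noise of SD 0.8 h), the raw bias was -4.8 h with r = 0.94; after calibration the bias in the same data was 0. Least squares guarantees that zero, so it says nothing about new subjects. Linear calibration also leaves r unchanged apart from sign, and r alone still does not give the remaining error, whose SD is s·√(1 − r²). At r = 0.90, √(1 − 0.81) = 0.436, so that SD is 0.87 h if s = 2 and 1.74 h if s = 4.

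**5. Precision of agreement measures.** With one value per subject and differences of SD 1 h, the 95% half-width is t/√n for the mean difference and about t·√(1/n + 1.96²/(2(n − 1))) for each limit of agreement. For n = 10 these are 0.72 h and 1.27 h; for n = 30, 0.37 h and 0.65 h. If the SD is 1.5 h, multiply by 1.5: about 1.1 h and 1.9 h at n = 10, and 0.6 h and 1.0 h at n = 30.

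**The case against.** The best defence is that 8.4 does not stop at a correlation. A 3-axis accelerometer does not record hours, so relating its output to the monitor is a sensible first step, and limits of agreement cannot be computed until the algorithm exists. The algorithm would be calibrated against the monitor and could remove a fixed shift or scale error. The study is also a descriptive pilot: 8.4 rules out formal hypothesis tests, and this is a secondary aim.

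Much of this stands. A reader might infer that the plan judges wear hours by correlation alone, so that a sensor wrong by more than the trial's own 2-hour limit would be declared valid. The documents do not support that. The correlation is of accelerometer data, not hours; a further testing step is planned; and no acceptance rule for r is stated. The 2-hour figure is a wear check, triggered when a subject is "wearing the GSM brace an average of 2 or more hours less per day than prescribed". It is read from the temperature monitor and is not an accuracy limit for the accelerometer. Section 5.4 makes the temperature monitor the primary means of tracking use, and 7.1 bases the primary wear measure on it, so accelerometer error cannot misdirect this trial's checks.

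The defence does not fill the gap in the testing step. Zero bias after calibration is automatic in the fitting data, and nothing in 8.4 says what will be measured or in whom. A descriptive pilot can report a descriptive error in hours as easily as a correlation.

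**Conclusion.** The point holds as a gap in specification and choice of statistic. As written, the analysis for secondary objective 3 cannot by itself show that estimated hours are accurate, because its one named statistic ignores constant and proportional error and varies with the spread of wear, and because its test of the algorithm is undefined.

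The insensitivity to shift and scale is algebra and rests on no assumption. The sizes (r of 0.85 to 0.99 alongside biases of 2.6 to 3.6 h; r of 0.55 to 0.96 for one and the same 1.5 h error SD) rest on assumed SDs and error patterns. They illustrate what r can hide and do not predict how this sensor behaves. The change is worth making before the analysis is run, but nothing in the primary aims depends on it.

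**What to change.** In 8.4, Secondary Aims 3:

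- Make the main result the difference between algorithm-estimated and temperature-monitor hours per subject-day. Obtain each subject's estimates from an algorithm fitted without that subject (leave-one-subject-out cross-validation).
- Report the mean difference and 95% limits of agreement in hours per day, with confidence intervals that allow for repeated days within subject, for example through a random subject effect.
- Add a calibration plot, as Appendix 1, section 8 already does for the smart pad.
- Keep the correlation as description only, and state its type and unit.
- Optionally report the share of subjects whose average differs by 2 h/day or more, labelled as a descriptive benchmark and not as an acceptance limit.

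The cost is a paragraph of text and a little more analysis. The paired sensor and monitor records are those the planned correlation already needs, so no new data are required. With 10 to 30 subjects the limits will be imprecise, and the confidence intervals will show by how much.
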